Erythrocytes (RBC)	Female	10 ¹² /L	< 2.0	NA
	Male	10 ¹² /L	< 2.5	NA
Lymphocytes		%	NA	> 80
Lymphocytes, abs		10 ⁹ /L	< 0.75	NA
Mean corpuscular volume (MCV)		fL	< 60	> 120
Monocytes		%	NA	> 30

8.5.3 Vital Signs and Weight

The measured vital signs include:

- Weight (kg).
- Body Temperature (degrees Celsius) and Route of Measurement.
- Systolic Blood Pressure (SBP [mmHg]), supine and standing.
- Diastolic Blood Pressure (DBP [mmHg]), supine and standing.
- Pulse Rate (bpm), supine and standing.

The following orthostatic vital signs will be calculated based on measurements in the supine and standing positions:

- Orthostatic SBP (mmHg) = Standing SBP – Supine SBP
- Orthostatic DBP (mmHg) = Standing DBP – Supine SBP
- Orthostatic Pulse Rate (bpm) = Standing Pulse Rate – Supine Pulse Rate

See Section 8.2.2 (Other Baseline Characteristics) for the derivations and conversions of the aforementioned variables. At each scheduled visit, preferably by the same observer, supine and standing SBP, DBP, and pulse rate will be measured using the same arm after the subject has been in the position for 2 minutes.

Potentially clinically significant (PCS) vital signs values will be identified. A vital sign value will be considered potentially clinically significant if it satisfies the criteria presented in Table 5 and is also more extreme than the subject's corresponding baseline value.

Table 5. Criteria for Identification of Potentially Clinically Significant (PCS) Vital Sign and Weight Values

Variable	Unit	Very Low (VL)	Very High (VH)
SBP ^a	mmHg	Value ≤ 90 and > 30 decrease from Baseline	Value ≥ 180 and > 40 increase from Baseline
DBP ^a	mmHg	Value ≤ 50 and > 30 decrease from Baseline	Value ≥ 105 and > 30 increase from Baseline
Pulse Rate ^a	bpm	Value ≤ 50 and > 30 decrease from Baseline	Value ≥ 120 and > 30 increase from Baseline
Temperature	°C	NA	Value ≥ 38.3 and ≥ 1.1 increase from Baseline
Orthostatic SBP (Hypotension)	mmHg	Decrease of ≥ 30 in SBP (supine to standing)	NA
Orthostatic DBP (Hypotension)	mmHg	Decrease of ≥ 20 in DBP (supine to standing)	NA
Weight	kg	Decrease of ≥ 7% from Baseline	Increase of ≥ 7% from Baseline

a. Both for supine and standing.

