8.2.2 Other Baseline Characteristics

Other Baseline characteristics include:

Vital Signs:

- Height (m) as measured during the Initial Screening Period
- Weight (kg)
- BMI (kg/m²)
- Body Temperature (degrees Celsius) including route of measurement
- Systolic Blood Pressure (SBP [mmHg]) supine, standing and orthostatic
- Diastolic Blood Pressure (DBP [mmHg]) supine, standing and orthostatic
- Pulse Rate (beats per minute [bpm]) supine, standing and orthostatic

Study specific calculations and/or conversions include:

Height (m): If applicable, height will be converted from inches to meters for the calculation of Body Mass Index (BMI), using the following formula:

$$\text{Height (m)} = (\text{XX inches} * 2.54)/100 \text{ and presented to two decimal precision.}$$

Weight (kg): If applicable, weight will be converted from pounds to kilograms for the calculation of BMI, using the following formula:

Weight (kg) = (XX pounds * 0.4536) and presented to one decimal precision.

Body Mass Index calculated as:

BMI (kg/m²) = Weight (kg)/Height (m)² and presented to one decimal precision.

Temperature (degrees Celsius): If applicable, temperature will be converted from degrees Fahrenheit to Celsius, using the following formula:

Temperature (degrees C) = (XX degrees F – 32)/1.8 and presented to one decimal precision.

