9.4.2 Other Baseline Characteristics

Default summary statistics, described in Section 6.0 (General Definitions, Methods, Naming Conventions and Data Handling), of the baseline subject characteristics will be presented for all countries/centers combined.

Subject Samples:	Tables	Safety sample and US Subset
	Listings	All subjects consented
	Figures	Not applicable
Subgroups:		Not applicable
Abbreviation:		SC

Standard Presentations

- SCT001 Other subject characteristics (SC) include the following vital signs:
- Systolic Blood Pressure (SBP [mmHg]), supine, standing, and orthostatic
 - Diastolic Blood Pressure (DBP [mmHg]), supine, standing, and orthostatic
 - Pulse rate (bpm), supine, standing, and orthostatic
 - Height (m)
 - Weight (kg), overall and by gender
 - BMI (kg/m²)
 - Body temperature (degrees Celsius)
 - Route of measurement

Standard subject data listings include:

- SCL001 The aforementioned vital signs data will be presented by subject. The relative day of the assessment will be calculated relative to the start of 3005 LCIG infusion (RFSTDTN) and will be presented for those subjects who received 3005 LCIG infusion.

Study Specific Presentations

- SCT002 Other subject characteristics include the following assessments collected during the Initial Screening Period:
- Duration in years since the first diagnosis of PD
 - Diagnosis of bradykinesia (slowness of initiation of voluntary movement with progressive reduction in speed and amplitude of repetitive actions)
 - Diagnosis of muscular rigidity
 - Diagnosis of 4 – 6 Hz resting tremor
 - Diagnosis of postural instability not caused by primary visual, vestibular, cerebellar or proprioceptive dysfunction

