9.11.3 Vital Signs

Subject Samples:	Tables	Safety sample
	Listings	All subjects consented
	Figures	Not applicable
Subgroups:		Not applicable
Abbreviation:		VS

Standard Presentations

- VST001 Summary of quantitative vital signs assessments will be presented, for all centers/countries combined, using default summary statistics. At each assessed visit, summary statistics will be presented as well as for the change from Baseline at each post-baseline visit.
- VST002 For each variable with a PCS criterion (as presented in [Table 5](#)), the incidence of PCS values will be presented. The percentage per parameter is defined as the ratio of the number of subjects with at least one PCS value occurring at a post baseline visit that is more extreme than their baseline value and the total number of subjects in the subject sample with a post baseline measurement of the specified parameter.

In addition, all vital signs data will be presented as follows:

- VSL001 A listing of PCS values together with standard demographic data will be presented by-subject and within-subject by PCS vital signs test criterion by visit.
- VSL002 Vital signs data will be presented by-subject and within-subject by vital signs test and visit.

Study Specific Presentations

- VST003 For each variable with a PCS criterion (as presented in [Table 5](#)), the incidence of PCS values will be presented by visit. For a specific visit, the percentage per parameter is defined as the ratio of the number of subjects with at least one PCS value occurring at a specific post-baseline visit that is more extreme than their baseline value and the total number of subjects in the subject sample with a post baseline measurement of the specified parameter for the visit.

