LBL002	14.3__4.4.3	Listing of Chemistry Determinations SAFETY SAMPLE – NARROW POLYNEUROPATHY SUBSET
VST001	14.3__5.1.1	Summary of Supine Systolic Blood Pressure (mmHg) SAFETY SAMPLE
VST001	14.3__5.1.2	Summary of Standing Systolic Blood Pressure (mmHg) SAFETY SAMPLE
VST001	14.3__5.1.3	Summary of Orthostatic Systolic Blood Pressure (mmHg) SAFETY SAMPLE
VST001	14.3__5.1.4	Summary of Supine Diastolic Blood Pressure (mmHg) SAFETY SAMPLE
VST001	14.3__5.1.5	Summary of Standing Diastolic Blood Pressure (mmHg) SAFETY SAMPLE
VST001	14.3__5.1.6	Summary of Orthostatic Diastolic Blood Pressure (mmHg) SAFETY SAMPLE
VST001	14.3__5.1.7	Summary of Supine Pulse (bpm) SAFETY SAMPLE
VST001	14.3__5.1.8	Summary of Standing Pulse (bpm) SAFETY SAMPLE
VST001	14.3__5.1.9	Summary of Orthostatic Pulse (bpm) SAFETY SAMPLE
VST001	14.3__5.1.10	Summary of Temperature (Celsius) SAFETY SAMPLE
VST001	14.3__5.1.11	Summary of Weight (kg) SAFETY SAMPLE
VST002	14.3__5.2.1	Number and Percent of Subjects with Potentially Clinically Significant Vital Sign Values SAFETY SAMPLE
VST003	14.3__5.2.2	Number and Percent of Subjects with Potentially Clinically Significant Vital Sign Values by Visit SAFETY SAMPLE
VSL001	14.3__5.2.3	Listing of Potentially Clinically Significant Vital Sign Parameters SAFETY SAMPLE
DCT005	14.3__6.1.1	Overview of Device Complications SAFETY SAMPLE
DCT006	14.3__6.1.2	Overview of Device Complications by 3005 Treatment Year SAFETY SAMPLE

SAP Table Code	Table Number	Table Title
DCT001	14.3__6.1.3	Number and Percent of Subjects with Device Complications by Type SAFETY SAMPLE
DCT002	14.3__6.1.4	Number and Percent of Subjects with Device Complications by MedDRA Preferred Term SAFETY SAMPLE
DCT003	14.3__6.1.5	Number and Percent of Subjects with Device Complications by MedDRA Preferred Term and 3005 Treatment Year SAFETY SAMPLE
DCT004	14.3__6.1.6	Number and Percent of Subjects with Device Complications by Action Taken SAFETY SAMPLE
DCT002	14.3__6.1.7	Number and Percent of Subjects with Device Complications with Action Taken of Tube Replacement by MedDRA Preferred Term SAFETY SAMPLE
DCT001	14.3__6.2.1	Number and Percent of Subjects with Device Complication Related to Adverse Events by Type SAFETY SAMPLE
DCT002	14.3__6.2.2	Number and Percent of Subjects with Device Complication Related to Adverse Events by MedDRA Preferred Term SAFETY SAMPLE

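### The SAP's orthostatic diastolic pressure formula subtracts supine systolic pressure, so every value is too low by the supine pulse pressure

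*SAP*

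**What the plan says.** SAP section 8.5.3 derives three orthostatic variables from supine and standing readings. The systolic line is "Orthostatic SBP (mmHg) = Standing SBP – Supine SBP", and the pulse line has the same form. The diastolic line between them is "Orthostatic DBP (mmHg) = Standing DBP – Supine SBP".

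Table 5, in the same section, has a row named Orthostatic DBP whose criterion is a fall in diastolic pressure on standing ("Decrease of ≥ 20 in DBP (supine to standing").

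Section 8.5.3 refers to section 8.2.2 for derivations, but 8.2.2 only lists the variable, "Diastolic Blood Pressure (DBP [mmHg]) supine, standing and orthostatic", with no orthostatic formula. Section 10.1, on changes to the planned analyses, does not mention it.

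The variable is reported in two places:

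- **Baseline table SCT001** (section 9.4.2): "Diastolic Blood Pressure (DBP [mmHg]), supine, standing, and orthostatic".
- **By-visit table VST001** (section 9.11.3), where "summary statistics will be presented as well as for the change from Baseline at each post-baseline visit". The list in section 12.2 names this output "Summary of Orthostatic Diastolic Blood Pressure (mmHg) SAFETY SAMPLE" (Table 14.3__5.1.6).

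The PCS tables VST002 and VST003 and the listing VSL001 apply the Table 5 criteria. VST002 counts subjects with "at least one PCS value occurring at a post baseline visit that is more extreme than their baseline value".

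**The concern.** A diastolic reading minus a systolic reading is not a postural change. It is strongly negative even in a subject whose pressure does not move on standing. Section 4.0 says the SAP is meant to guide programming for both the October 2015 interim analysis and the final report, and a derivation formula is what a programmer copies.

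Long-term safety is the primary statistical objective (protocol section 13.1), and protocol section 10.8 itself names postural hypotension with levodopa combinations. Two reported summaries of orthostatic diastolic pressure are at stake, and possibly the PCS counts. No efficacy or adverse event analysis uses the variable.

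**Working it through.** The plan gives no numerical result to reproduce, so the check is algebra followed by illustration. The formulas and the -20 mmHg threshold come from SAP section 8.5.3. The documents contain no blood pressure data, so all readings and distributions below are assumptions.

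**Identity (no assumption needed).**

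Printed value = standing DBP - supine SBP = (standing DBP - supine DBP) - (supine SBP - supine DBP).

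So printed value = true postural change - supine pulse pressure.

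**Worked readings.**

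| Supine | Standing DBP | Printed formula | Correct formula |
|---|---|---|---|
| 120/80 | 80 | 80 - 120 = -40 | 80 - 80 = 0 |
| 130/80 | 78 | 78 - 130 = -52 | 78 - 80 = -2 |
| 115/72 | 70 | 70 - 115 = -45 | 70 - 72 = -2 |
| 130/80 | 60 | 60 - 130 = -70 | 60 - 80 = -20 |

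The first three pass a -20 threshold as printed although diastolic pressure fell by 2 mmHg at most. Only the fourth is a true 20 mmHg fall.

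**Change from baseline.** If supine pulse pressure rises from 50 to 60 with no postural change at either visit, the printed formula gives -60 - (-50) = -10 mmHg. The correct change is 0.

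**Size under assumed distributions.** There are 3 × 2 × 3 × 3 × 2 = 108 scenarios, with 60,000 simulated subjects each:

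- mean supine pressure 115/72, 128/78 or 140/80, SD 18/10;
- systolic-diastolic correlation 0.5 or 0.7;
- true postural diastolic change with mean 0, -2 or -5 and SD 7, 8 or 10;
- within-subject correlation between visits 0.3 or 0.6.

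*Means.* Assumed mean pulse pressures are 43, 50 and 60. The printed formula therefore averages from 0 - 43 = -43 to -5 - 60 = -65 mmHg, against 0 to -5 when correct.

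*SD of change from baseline, central case* (128/78, correlation 0.5, postural SD 8, between-visit correlation 0.6). The pulse pressure variance is 18² + 10² - 2(0.5)(18)(10) = 244. The printed formula gives √(244 + 8²) × √(2 × 0.4) = 15.7 mmHg. The correct formula gives 8 × √0.8 = 7.2 mmHg. Over all scenarios the ranges are 13 to 22 against 6 to 12 mmHg.

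**PCS flag, only if the threshold is applied to the derived variable.** A flag needs a value of -20 or lower that is also below the subject's baseline.

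| Post-baseline visits | Flagged, printed formula | Flagged, correct formula |
|---|---|---|
| 1 | 47-49% | 0.2-7% |
| 4 | 78-80% | 1-21% |
| 8 | 88-89% | 1-34% |

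As printed, nearly every value is below -20, so the flag reduces to having any visit below baseline. When baseline and follow-up values are exchangeable, that probability is k/(k+1) for k visits: 50%, 80% and 89%. The simulation sits just under these limits.

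**The case against.** The best defence is that this is an evident slip whose correction lies beside it. The neighbouring formulas and Table 5 leave only one coherent reading. Literal programming would also be conspicuous: supine, standing and orthostatic diastolic pressure are consecutive outputs (Tables 14.3__5.1.4 to 14.3__5.1.6), and a mean near -50 mmHg would look odd next to supine and standing means a few mmHg apart. Those two tables and the orthostatic systolic table are defined correctly, so a postural fall would still be visible. The variable is descriptive and no alpha level is tested.

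All of that is fair, and it limits the seriousness. Some cautions on the numbers also stand:

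- The mean and SD ranges follow from the chosen inputs.
- The PCS percentages describe one of two possible programming routes. Table 5 programmed from its own wording gives the right flag.
- The k/(k+1) limit fails if pulse pressure trends over time.
- Section 6.4.8 evaluates every reported measurement for PCS, not one per visit.
- Eight visits is an assumption: six-monthly visits over the protocol's approximate 4 years, whereas individual follow-up will vary.

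None of this makes the printed line correct. It is the operative and only derivation of the variable, and relying on someone to notice an odd table is weaker than correcting the formula.

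**Conclusion.** The formula is wrong as written and should be corrected. That conclusion, and the size of the error per reading (minus the supine pulse pressure), rest on algebra alone.

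If the line is followed, the orthostatic diastolic results in SCT001 and Table 14.3__5.1.6 are wrong in both level and change from baseline. The effect on VST002, VST003 and VSL001 is conditional, because the Table 5 row carries the name of the wrongly derived variable but states the criterion correctly in words. The simulated ranges show direction and rough scale only. The documents do not show whether any program used the printed line.

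**What to change.** In SAP section 8.5.3, change the line to: Orthostatic DBP (mmHg) = Standing DBP – Supine DBP. Supine diastolic pressure is already collected, so nothing else is needed to compute it.

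In Table 5, add a phrase saying that the Orthostatic DBP criterion is this variable at or below -20 mmHg. This leaves the threshold unchanged and removes the ambiguity for the PCS outputs. It is helpful rather than essential once the formula is right, and the orthostatic SBP row could be worded in the same style.

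Then check whether the derived vital signs data or any interim output was built from the printed line, and rerun only what was. The document cost is one word and one phrase. A rerun is needed only if that check finds an affected output.

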8.5.4 Electrocardiogram (ECG) Data

In Study 3005, single standard 12-lead electrocardiograms (ECGs) are to be performed as an element of routine care and are done as a subject's condition mandates. The final visit is the only study visit at which an ECG is one of the scheduled assessments. All ECGs are to be reviewed by a local reader, who assesses them as "Normal," "Abnormal, not clinically significant," "Abnormal, clinically significant" or "Unknown." Clinically significant abnormalities in the ECG are to be reported as an AE and the subject's ECG is to be repeated at medically appropriate intervals until it stabilizes or returns to acceptable levels. Due to the limited data collected, ECG results and interpretations will be presented as a listing but will not be summarized.

8.5.5 Other Safety Analyses

Other safety data, not previously discussed, include:

- Complications with infusion device
- PEG tube and J tube replacements and average duration
- Sleep attacks
- Minnesota Impulsive Disorders Interview (MIDI)
- Columbia Suicide Severity Rating Scale (C-SSDRS)
- Melanoma check
- Neurological examination

8.5.5.1 Complications with Infusion Device

For each complication related to the infusion device (i.e., tubing kinks, tubing displaced, tubing connector problems, and pump technical difficulties) the following data will be collected in addition to a description of the complication.

- Incident start and stop date
- Type of complication
 - Pump complication

- Intestinal tube complication
- PEG-J complication
- Stoma complication
- Other complication
- Action taken
 - No action taken
 - Reposition of tube with surgery
 - Reposition of tube without surgery
 - Pump replaced
 - Medication treatment interrupted
 - Medication treatment stopped
 - Other
- Did this complication result in an AE? ("Yes" or "No")
- For complications that resulted in an AE, the AE number(s)

Each device complication will be assigned to a Preferred Term (PT), according to the MedDRA thesaurus, Version 14.0.

The percentage of subjects with a device complication will be determined as the number of subjects with at least one device complication relative to the number of subjects at risk. A subject will be considered at risk if the subject is in the Safety subject sample. Summaries of device complications by action taken will exclude complications where the response for action taken is "No action taken."

The incidence of device complications during each 3005 Treatment Year will be summarized using the study day intervals described in Section 6.4.9. Device complication start days and Treatment Period end days will be calculated relative to the start of 3005 LCIG infusion (RFSTDTN) as follows:

$$\text{Device Complication Start Day} = (\text{Device Complication Start Date} - \text{Date of First 3005 LCIG Infusion}) + 1$$

$$\text{Treatment Period End Day} = ([\text{Date of Last 3005 PEG-J Exposure} + 30 \text{ Days}] - \text{First Date of 3005 LCIG Infusion}) + 1$$

The count (and numerator for percentage calculations) will be the number of subjects who had their first occurrence of the PT start within the study day range for the 3005 Treatment Year. Each subject will be counted at most once within each SOC and PT.

The denominator for percentage calculations will include all subjects whose Treatment Period End Day is within or greater than the study day range for the 3005 Treatment Year.

8.5.5.2 PEG Tube and J Tube Replacements and Average Duration

The date of each PEG tube and J tube placement and removal is recorded on the Device Information eCRF. The number of PEG tube replacements and the number of J tube replacements overall and by 3005 Treatment Year will be summarized.

The number of PEG tube and J tube replacements during each 3005 Treatment Year will be summarized using the study day intervals described in Section 6.4.9. Tube replacement days and Treatment Period end days will be calculated relative to the start of 3005 LCIG infusion (RFSTDTN) as follows:

$$\text{Tube Replacement Day} = (\text{Tube Placement Date} - \text{Date of First 3005 LCIG Infusion}) + 1$$

$$\text{Treatment Period End Day} = ([\text{Date of Last 3005 PEG-J Exposure} + 30 \text{ Days}] - \text{First Date of 3005 LCIG Infusion}) + 1$$

The count (and numerator for percentage calculations) will be the number of subjects who had one or more PEG (or J) tube replacements within the study day range for the 3005 Treatment Year. Each subject will be counted at most once for each 3005 Treatment Year.

The denominator for percentage calculations will include all subjects whose Treatment Period End Day is within or greater than the study day range for the 3005 Treatment Year.

As previously described, Study 3005 is an extension of the previous Studies 3001, 3002, 3003, and 3004. The number of PEG tube and J tube replacements in these previous studies will be retrieved from the relevant study databases and will be summarized.

The average PEG tube and J tube duration (time in place) during Study 3005 will be summarized. For each tube the duration will be calculated as the tube removal date – the tube placement date +1. The average PEG tube and average J tube duration for each subject will then be calculated as the mean of all PEG (J-tube) tubes the subject had exposure to during the study. For tubes already in place at the start of the study (missing placement date), the placement date will be imputed as the date of the first 3005 LCIG infusion (as defined in Section 6.4.1). For tubes remaining in place (missing removal date), the removal date will be imputed as the date of the last 3005 PEG-J exposure (as defined in Section 6.4.1). Due to the imputation of placement and removal dates, the 3005 tube duration will be interpreted as the minimal amount of time the tube was in place.

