6.1 General Methodology and Presentation

The default summary statistics for quantitative variables will be the number of observations (n), mean, standard deviation (SD), median, minimum (min) and maximum (max), for those subjects with data.

All summary statistics will be rounded (using the SAS[®] function ROUND) and presented to one more decimal place than the raw value, except for the minimum and maximum values that will be presented with the same decimal precision as the raw value.

For qualitative variables, the number (n) and percentage (%) of subjects with non-missing data per category will be the default summary presentation, and where appropriate and present, the number of missing values as a "Missing" category.

Percentage values are to be rounded and presented to one decimal place, for example, 52.3%. If the calculated percentage is > 0.0% but < 0.1% then < 0.1% is to be presented in the relevant table and/or listing.

The exceedance probabilities for testing the null hypothesis will be denoted by "*P* value." *P* values are to be rounded (using the SAS[®] function ROUND) and printed with three decimals. *P* values below 0.0005 will be denoted as < 0.001.

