9.11.5 Other Safety Analyses

Other safety analyses will include device complications, PEG and J tube replacements and average duration, the sleep attack questions, Minnesota Impulsive Disorder Interview (MIDI), Columbia Suicide Severity Rating Scale (C-SSRS), melanoma check and neurological examination. Device complications will be reported on a per-subject basis. This implies that even if a subject reported the same complication repeatedly (complications that map to the same PT or that result in the same action taken), the complication will be counted only once.

Subject Samples:	Tables	Safety sample and US subset of safety sample
	Listings	All subjects consented
	Figures	Not applicable
Subgroups:		Not applicable
Abbreviation:		DC, DI, PE, QS

Study Specific Presentations

- DCT001 The incidence of device complications overall and by complication type will be presented, for all centers/countries combined, using default summary statistics. A table will be produced for all device complications as well as for the subset of device complications that resulted in an AE.
- DCT002 The incidence of device complications overall and for each MedDRA PT will be presented, for all centers/countries combined, using default summary statistics. A table will be produced for all device complications as well as for the subset of device complications that resulted in an AE.

- DCT003 The incidence of device complications overall and for each MedDRA PT will be summarized within each 3005 Treatment Year (as defined in Section 6.4.9), for all centers/countries combined, using default summary statistics. A table will be produced for all device complications as well as for the subset of device complications that resulted in an AE.
- DCT004 The incidence of device complications overall and for each action taken will be presented, for all centers/countries combined, using default summary statistics. A table will be produced for all device complications as well as for the subset of device complications that resulted in an AE.
- DCT005 Overview of Device Complications including the number of subjects with:
- At least one device complication
 - At least one device complication with action taken of tube replacement (either with or without surgery)
 - At least one device complication with an associated adverse event
 - At least one device complication with an associated adverse event and action taken of tube replacement (either with or without surgery).

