- DCT006 Overview of Device Complications (same categories as DCT005) for each 3005 Treatment Year (as defined in Section 6.4.9).
- DIT001 A summary of PEG tube replacements will be presented, for all centers/countries combined, using default summary statistics. A similar summary will be presented for J tube replacements.
- DIT002 A summary of PEG tube and J tube replacements will be presented for each 3005 Treatment Year (as defined in Section 6.4.9).
- DIT003 The average PEG tube and J tube duration in Study 3005 will be summarized with default summary statistics and with the number and percentage of subjects with average durations in 3 month time intervals (≤ 91 days, 92 – 182 days, 183 to 273 days, 274 to 365 days, or > 365 days).
- QST001 A summary of sleep attacks will be presented, for all centers/countries combined, using default summary statistics.

- QST002 A summary of the development of intense impulsive behavior as assessed by the Minnesota Impulsive Disorders Interview (MIDI) will be presented, for all centers/countries combined, using default summary statistics.
- QST003 A summary of suicidal ideation and behavior as assessed by the Columbia Suicide Severity Rating Scale (C-SSRS) will be presented, for all centers/countries combined, using default summary statistics.

In addition, the other safety analysis data will be presented as follows:

- DCL001 A listing of device complications with the standard demographic data will be presented by-subject.
- DIL001 A listing of device information with the standard demographic data will be presented by-subject.
- PEL001 A listing of results of melanoma checks with the standard demographic data will be presented by-subject and within-subject by visit.
- QSL008 A listing of sleep attack responses with the standard demographic data will be presented by-subject and within-subject by visit.
- QSL009 A listing of MIDI responses and positive/negative assessment for impulsive behavior with the standard demographic data will be presented by-subject and within-subject by visit.
- QSL010 A listing of C-SSRS responses with the standard demographic data will be presented by-subject and within-subject by visit.

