DCT003	14.3__6.2.3	Number and Percent of Subjects with Device Complication Related to Adverse Events by MedDRA Preferred Term and 3005 Treatment Year SAFETY SAMPLE
DCT004	14.3__6.2.4	Number and Percent of Subjects with Device Complication Related to Adverse Events by Action Taken SAFETY SAMPLE
DCT002	14.3__6.3.1	Number and Percent of Subjects with Device Complication by MedDRA Preferred Term SAFETY SAMPLE – US SUBSET
DCT002	14.3__6.3.2	Number and Percent of Subjects with Device Complication Related to Adverse Events by MedDRA Preferred Term SAFETY SAMPLE – US SUBSET
DIT001	14.3__6.4.1.1	Number of PEG Tube Replacements SAFETY SAMPLE
DIT001	14.3__6.4.1.2	Number of J Tube Replacements SAFETY SAMPLE
DIT002	14.3__6.4.2	Number of PEG Tube and J Tube Replacements by 3005 Treatment Year SAFETY SAMPLE
DIT001	14.3__6.4.3.1	Number of PEG Tube Replacements before 3005 Study Start SAFETY SAMPLE
DIT001	14.3__6.4.3.2	Number of J Tube Replacements before 3005 Study Start SAFETY SAMPLE
DIT003	14.3__6.4.4.1	Average PEG Tube Duration in Study 3005 SAFETY SAMPLE
DIT003	14.3__6.4.4.2	Average J Tube Duration in Study 3005 SAFETY SAMPLE

SAP Table Code	Table Number	Table Title
QST001	14.3__7.1	Summary of Sleep Attacks SAFETY SAMPLE
QST002	14.3__7.2	Summary of Minnesota Impulsive Disorder Interview (MIDI) SAFETY SAMPLE
QST003	14.3__7.3	Summary of Columbia Suicide Severity Rating Scale (C-SSRS) SAFETY SAMPLE

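### The by-year table of PEG and J tube replacements counts subjects rather than replacements, and no device-complication table gives an event count or a rate

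*SAP*

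**What the plan says.** **Tube replacements by year.** SAP 8.5.5.2 first states the deliverable: "The number of PEG tube replacements and the number of J tube replacements overall and by 3005 Treatment Year will be summarized". It then defines the by-year entry differently: "The count (and numerator for percentage calculations) will be the number of subjects who had one or more PEG (or J) tube replacements within" the day range of that year, and adds "Each subject will be counted at most once for each 3005 Treatment Year". SAP 12.2 still titles Table 14.3__6.4.2 (DIT002) "Number of PEG Tube and J Tube Replacements by 3005 Treatment Year". The denominator is every subject whose Treatment Period End Day falls in or after the year's day range.

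**Tube replacements overall.** This is a separate table, DIT001. SAP 9.11.5 says: "A summary of PEG tube replacements will be presented, for all centers/countries combined, using default summary statistics", with a similar J tube version. SAP 12.2 lists both for Study 3005 and for the time before it. The once-per-year rule is not attached to DIT001. DIT003 summarises each subject's average tube duration, and DIL001 lists device information by subject.

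**Device complications.** SAP 9.11.5 reports these per subject: when repeats share a PT or an action taken, "the complication will be counted only once". For the by-year PT table, SAP 8.5.5.1 counts only a subject's first occurrence of the PT. DCT005 and DCT006 are described as numbers of subjects. No table in SAP 12.2 is described as giving a number of complications or a rate. Individual records appear in listing DCL001.

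**The concern.** Monitoring device complications is one of the listed safety assessments (Protocol 6.2, SAP 7.2). Long-term safety is the primary statistical objective (Protocol 13.1), and causality is judged over drug, device and implantation procedure together (Protocol 12.1.1). A tube can be changed more than once in a year, and the same complication can recur in the same subject.

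Someone reading DIT002 by its title would take subjects for replacements. The shortfall grows with the replacement rate, so differences between years are compressed most where replacement is most frequent. For complications, no summary table separates a subject with one event of a given PT from a subject with ten.

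**Working it through.** **Inputs.** The documents state no replacement or complication rate, so there is no plan figure to reproduce. The planned size, about 275 (Protocol 7.1, SAP 5.2), is used only for scale. The rates r below, per subject-year, are assumptions, as is full-year follow-up.

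**Step 1: two data sets, one printed result.** Take 275 subjects. In case A, 100 of them have one replacement each in Year 1 (100 replacements). In case B, 100 have three each (300 replacements). DIT002 prints 100/275 = 36.4% for both. If DIT001 summarises the number per subject, and there are no other replacements, it separates them: mean 100/275 = 0.364 against 300/275 = 1.091, maximum 1 against 3.

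**Step 2: how much a yearly subject count omits.** Expected replacements are 275 × r.
- Poisson, one common rate: subjects with at least one = 275 × (1 − e^(−r)); share not shown = 1 − (1 − e^(−r))/r.
- Rates varying between subjects (gamma-Poisson, frailty variance 1): subjects with at least one = 275 × r/(1 + r); share not shown = r/(1 + r).

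| Assumed r | Replacements | Subjects, Poisson | Not shown | Subjects, gamma-Poisson | Not shown |
|---|---|---|---|---|---|
| 0.1 | 27.5 | 26.2 | 4.8% | 25.0 | 9.1% |
| 0.25 | 68.8 | 60.8 | 11.5% | 55.0 | 20.0% |
| 0.5 | 137.5 | 108.2 | 21.3% | 91.7 | 33.3% |
| 1.0 | 275.0 | 173.8 | 36.8% | 137.5 | 50.0% |
| 2.0 | 550.0 | 237.8 | 56.8% | 183.3 | 66.7% |

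**Step 3: the last row of DIT002.** The class beyond Year 5 is open-ended (after day 1825, SAP Table 3), while visits run to Month 84, target day 2520 (SAP Table 2). Up to that target day, 2520 − 1825 = 695 days, about 1.9 years, fall under one at-most-once count.

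**Step 4: complications by year (DCT003).** Under the first-occurrence rule a repeat of the same PT in a later year is dropped too, while the subject stays in the denominator. With a constant assumed yearly risk p, independent years and no dropout, the share shown in year y is p(1 − p)^(y−1). For p = 30%, Years 1 to 5 show 30.0%, 21.0%, 14.7%, 10.3% and 7.2%. The fall comes from the counting rule alone.

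**The case against.** The best defence is that per-subject incidence is the SAP's declared convention for adverse events (9.11.1) and for device complications (9.11.5). The study is single-arm and descriptive, with no alpha (Protocol 13.4). The rule in 8.5.5.2 is explicit enough to program, so on this view a new title for DIT002 would be enough.

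Several parts of this stand. A reader might infer that tube replacements are counted once per subject for the whole study, or that recurrent tube failure cannot be seen at all. The documents support neither reading:
- The limit is once per subject per Treatment Year and governs DIT002 only. A subject with replacements in Years 1, 2 and 4 appears in all three.
- DIT001 covers the overall number. If it is quantitative, n × mean divided by the PEG-J subject-years in EXT001 gives a crude overall rate.
- Repeated replacement shortens the average duration in DIT003, and DIL001 and DCL001 hold the records.
- Replacement is not failure. Its frequency depends on tube condition and local practice (Protocol 10.1.2).

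A reader might also infer that the percentages saturate. At 0.5, 1.0 and 2.0 events per subject-year over 4 years, 1 − e^(−4r) gives 86.5%, 98.2% and 99.97% ever affected. DIT002 restarts each year and does not produce that quantity. For complications it fits at most the row for any complication, and the rates are assumed.

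Other parts do not answer the point. DIT001 has no by-year or exposure-adjusted form. Its layout is also open, because the SAP uses the same default-statistics wording for percentage tables such as DCT001. DIT003 rests on imputed dates: a subject who leaves at day 80 with the original tube falls in the same lowest class (up to 91 days) as one whose tubes are changed every 80 days. Complications have no counterpart to DIT001, nor to the by-year prevalence table that adverse events have (AET014).

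**Conclusion.** The point holds in two parts. First, SAP 8.5.5.2 and the title of DIT002 promise a number of replacements by year, while the rule yields a number of subjects; repeats within a year are not shown by year. Second, every device-complication table counts subjects, and repeats are visible only in DCL001.

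The contradiction and the missing event counts are read directly from the SAP and need no assumption. Their size does. Under Poisson rates with full-year follow-up, DIT002 would omit about 5% of replacements at 0.1 per subject-year and 57% at 2.0, and more if some subjects are prone to repeats. If replacement is rare, the loss is small. This is more than a labelling matter, because the by-year quantity the SAP promises is absent and the device-safety assessment has no summary of recurrence. It does not make recurrent replacement invisible overall, and a replacement count should not be presented as a failure count.

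**What to change.** - **DIT002:** for PEG and J tubes separately, show the total number of replacements and the rate per subject-year of PEG-J exposure falling in each Treatment Year, next to the number of subjects with at least one. Retitling alone would remove the contradiction but leave the promise in 8.5.5.2 unmet.
- **DIT001:** state that the variable is the number of replacements per subject.
- **DCT001 to DCT003:** add the number of events and events per subject-year. In DCT003 count every occurrence in the year for these columns. Footnote that counts depend on sites entering repeats as separate records.
- **Intervals, if given:** allow for repetition within subject, with a robust variance or a negative binomial model.
- **Related reconciliation:** DCT005, DCT006 and Table 14.3__6.1.7 use an action of tube replacement, whereas the action list in SAP 8.5.5.1 offers only repositioning of the tube.

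The cost is a few extra columns. Tube placement dates, complication start dates and PEG-J exposure dates are already in the planned data. The added work is splitting each subject's exposure across Treatment Years.
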